8.2.3 Assessment of Disease Response and Progressive Disease

- On-trial imaging will be performed at Week 6 (-7 days), every 6 weeks (±7 days) for 50 weeks, and every 12 weeks (±7 days) thereafter from the date of first dose until PD is assessed by the investigator (unless the investigator elects to continue treatment and follow iRECIST beyond RECIST PD), the start of new anticancer therapy, withdrawal of consent, or death, whichever occurs first. Imaging assessments should follow calendar days and should not be adjusted for delays in cycle starts. If imaging shows PD, then a subsequent imaging assessment, in clinically stable subjects only, should be performed within 4 to 7 weeks to confirm PD if following iRECIST. Imaging is not required when subject is in survival follow-up.
- Imaging assessments should be scheduled using the date of first dose as the reference date (not the date of the previous tumor assessment) and should be respected regardless of whether trial treatment is temporarily withheld, or unscheduled assessments performed.
- The reading of the scans will be done by a local radiologist. To the greatest extent possible, sites should maintain the same radiologist throughout the trial. Results from the radiology

evaluations are to be recorded, and a copy of the evaluation reports should be kept in the subject's file. RECIST 1.1 criteria will be used for secondary endpoint response evaluation (Eisenhauer et al., 2009) and Appendix 7; iRECIST will be used for exploratory endpoint response evaluation (Seymour et al., 2017).

- Additional CT or MRI scans may be performed at the investigator's discretion to confirm response or new symptoms. Tumor imaging to confirm PR or CR should be performed at least 4 weeks after the first indication of a response is observed. In this case, the investigator must choose the imaging technology based on the clinical indication.
 - If an off-schedule imaging assessment is performed because progression is suspected, subsequent imaging assessments should be performed in accordance with the original imaging schedule.
 - Additional imaging assessments may be performed at any time during the trial at the investigator's discretion to support the efficacy evaluations for a subject, as necessary. Clinical suspicion of PD at any time requires a physical examination and imaging assessments to be performed promptly rather than waiting for the next scheduled imaging assessment.

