9 STATISTICAL CONSIDERATIONS

The statistical analysis of the data collected in this trial is the responsibility of the sponsor. A description of the statistical methods to be used to analyze the data is outlined below. The analyses will be detailed further in the SAP.

The SAP will be developed and finalized before database lock and will describe the subject populations to be included in the analyses, and procedures for accounting for missing, unused, and spurious data. This section is a summary of the planned statistical analyses of the primary and secondary endpoints.

All presentations will be done separately for the Dose Escalation part and the Expansion part. Subjects in the Dose Escalation part will typically be analyzed according to the DL received. Subjects in the Expansion part will be analyzed according to their assigned Expansion cohort. Exploratory analyses may be considered for HNSSC subjects crossing over from GEN1053 to GEN1053+IM due to PD.

The main analyses will be timed as follows:

- Interim analysis, Monotherapy Dose Escalation phase 1a and Combination therapy Dose Escalation phase 1b: Main safety and pharmacodynamic analyses will be conducted on all subject data at the end of the escalation (upon completion of DLT evaluation of the last subject in the Escalation phase).
- **Primary analysis, Expansion phase 2a**: The Expansion part consists of parallel cohorts, wherein each Expansion cohort may report its individual main analysis. Main safety, pharmacodynamic and efficacy analyses will be conducted at the time all subjects who are still receiving trial treatment have at least 2 postbaseline scans performed (such that the exploratory efficacy endpoints can be assessed) or have completed the safety follow-up period or have ended the trial.

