9.4.2.1.1 Objective Response Rate

The confirmed ORR is defined as the proportion of subjects with BOR of confirmed CR or confirmed PR (ie, "responders"), as per local review and according to RECIST v1.1. Repeat imaging may be performed no less than 4 weeks after the criteria for CR or PR are met to confirm the initial response.

An assessment of SD requires at least 5 weeks from C1D1 to scan date.

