9.5 Efficacy Monitoring in Expansion Cohorts

The Expansion part will be conducted in at least 2 tumor types using the Bayesian PPoS with a maximum sample size of 40 per indication and treatment (both mono- and combination therapy).

The efficacy in each Expansion cohort will be monitored utilizing the Bayesian efficacy monitoring via predictive probabilities (Lee and Liu, 2008). In particular, the PPoS will be calculated when (at minimum) 2 scans from the first 10 subjects in the Expansion cohort have been locally reviewed. The next futility inspection takes place when data from 20 subjects have been locally reviewed.

At the end of the Expansion cohort, the success criteria are defined as the posterior probability that the confirmed ORR exceeds the ineffective ORR threshold (p_0) with at least 80%. The weights correspond to how likely each outcome is.

If the predicted probability of success is less than 10% the monotherapy Expansion cohort is judged as likely being "futile." However, the threshold of 10% is not considered as a binding futility bar as the Expansion cohort at this stage still is under explorative investigation. The enrollment into the Expansion cohort may also continue (up to maximum 40 subjects) while the scans necessary to derive the response rates in the initial 20 subjects are obtained and reviewed. For the combination therapy Expansion cohort, a 30% threshold determines whether further investigation is judged "futile" or "non-futile." However, again, the criterion is nonbinding.

The ineffective ORR thresholds are tabulated in Table 9-2, with the rates considered to warrant further evaluation of GEN1053 as mono- or combination therapy (p_1) . Based on p_0 , the number of responders required at the monitoring time to consider the data as a likely "success" (by each case) is presented in Table 9-3.

For calculations, the Bayesian Efficacy Monitoring via Predictive Probability application v1.1.4 at www.trialdesign.org has been utilized, based on the following design parameters:

- Beta(p₀,1-p₀) as prior distribution for the response rate
- No early stopping for efficacy

Table 9-2The Ineffective ORR Threshold and the Response Rates That Warrant
Further Evaluation of the Drug

Cancer Type	Case A: Mono Therapy HNSCC	Case B: Combination Therapy NSCLC	
$\begin{array}{l} \text{Ineffective ORR threshold} \\ (\text{ORR} \leq p_0) \end{array}$	p ₀ =10%	p ₀ =15%	
ORR that warrants further evaluation of the drug	p1=25%	p1=30%	

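### The first futility look in Section 9.5 can run before a Week 12 response can be confirmed, and the plan does not say how a pending response enters the predictive probability

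*Combined protocol and SAP*

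**What the plan says.** - **Trigger.** Section 9.5: "the PPoS will be calculated when (at minimum) 2 scans from the first 10 subjects in the Expansion cohort have been locally reviewed". The next look is at 20 subjects. No scan count is given for it, but enrollment may continue "while the scans necessary to derive the response rates in the initial 20 subjects are obtained and reviewed".
- **Endpoint.** Section 9.5: at the end of the cohort, "the success criteria are defined as the posterior probability that the confirmed ORR exceeds the ineffective ORR threshold", with a posterior cut of 80%. Section 9.4.2.1.1: "The confirmed ORR is defined as the proportion of subjects with BOR of confirmed CR or confirmed PR".
- **Imaging.** Section 8.2.3: "On-trial imaging will be performed at Week 6 (-7 days), every 6 weeks (±7 days) for 50 weeks", and "Tumor imaging to confirm PR or CR should be performed at least 4 weeks after the first indication of a response is observed".
- **Force of the rule.** Futility means PPoS below 10% (HNSCC monotherapy) or below 30% (NSCLC combination). Both are nonbinding; for the combination cohort the text reads "However, again, the criterion is nonbinding". The synopsis places the futility analysis after 10 and/or 20 subjects and says that the estimate is updated as data come in.
- **Counting.** No section says how an unconfirmed CR or PR is treated at a look. Section 9.4.2.1 calls subjects with CR or PR objective responders without mentioning confirmation; Section 9.4.2.1.1 reserves the term responder for confirmed ones.
- **Table 9-3.** HNSCC: N/A at 10 subjects, at least 2/20, at least 6/40. NSCLC: at least 2/10, 4/20 and 9/40. The printed futile and success rates are, for HNSCC, 48% and 17% at ORR 10% and 7% and 91% at ORR 25%; for NSCLC, 72% and 10% at ORR 15% and 19% and 76% at ORR 30%.

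**The concern.** The trigger and the endpoint run on different clocks. Two postbaseline scans are Weeks 6 and 12. A Week 6 response can be confirmed at Week 12, but a Week 12 response needs a further scan. For the most recently enrolled of the first 10 subjects, the look can therefore fall while a response is still open. With 10 subjects, one response decides the call, so the unstated treatment of that subject can decide it too. At stake are the futile or non-futile label attached to a cohort and the published operating characteristics, which describe a look at which nothing is pending.

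**Working it through.** **Inputs.** From Section 9.5 and Tables 9-2 and 9-3: maximum n = 40; prior Beta(p0, 1−p0) with p0 = 0.10 (HNSCC) and 0.15 (NSCLC); posterior cut 0.80; PPoS thresholds 10% and 30%; looks at 10 and 20.

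**1. Final cut-off.** This is the smallest r with P(p > p0 | Beta(p0 + r, 1 − p0 + 40 − r)) ≥ 0.80.
- NSCLC: 0.775 at r = 8 and 0.877 at r = 9, so 9/40.
- HNSCC: 0.648 at r = 5 and 0.807 at r = 6, so 6/40.

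Both match Table 9-3.

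**2. PPoS.** PPoS(x, n) = P(x + Y ≥ r), where Y is beta-binomial with 40 − n trials and parameters p0 + x and 1 − p0 + n − x.

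| Cohort (threshold) | Look at 10 | Look at 20 |
|---|---|---|
| NSCLC (30%) | 1/10: 9.8%; 2/10: 38.1% | 3/20: 13.2%; 4/20: 37.0% |
| HNSCC (10%) | 0/10: 0.7%; 1/10: 24.7% | 1/20: 2.8%; 2/20: 18.5% |

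**3. Reproducing the printed rates.** Exact binomial enumeration, with every response known at each look:
- NSCLC (2/10, 4/20, 9/40): futile 72.0% and success 9.6% at ORR 15%; 19.2% and 76.3% at ORR 30%. This matches the table.
- HNSCC with a rule of at least 1/10 at the first look: 48.4% and 17.5% at ORR 10%; 6.7% and 90.6% at ORR 25%. This agrees with the table to within 1 point.
- HNSCC with no look at 10, as N/A implies: 39.2% and 19.3% at ORR 10%; 2.4% and 94.3% at ORR 25%. This does not match.

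**4. Timing.** A response first seen at Week 12 plus at least 4 weeks gives Week 16 with an extra scan, or Week 18 on schedule. That is a third postbaseline scan.

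**5. Size if pending responses count as non-response.** Two inputs are assumptions that the documents do not give:
- A share f = 80-90% of confirmed responders is first seen at scan 1, the rest at scan 2.
- Accrual runs from one subject per 2 weeks to one per week. When subject 10 reaches Week 12, subjects who entered at least 6 weeks earlier have had scan 3: 7 of 10 at the slower rate, 4 of 10 at the faster.

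A subject with three scans counts with probability p, a subject with two scans with probability f·p. NSCLC at p = 0.30, f = 0.8, 4 of 10 mature (so 0.8 × 0.30 = 0.24 for the other six):
- P(0) = 0.7⁴ × 0.76⁶ = 0.046
- P(1) = 4 × 0.3 × 0.7³ × 0.76⁶ + 0.7⁴ × 6 × 0.24 × 0.76⁵ = 0.079 + 0.088
- P(futile at 10) = 0.213, against 0.149 with all responses known

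| f | Mature at look | Futile at 10 | Futile at any interim, 20-subject look mature |
|---|---|---|---|
| 1.0 | any | 14.9% | 19.2% |
| 0.9 | 7/10 | 16.4% | 20.4% |
| 0.9 | 4/10 | 17.9% | 21.8% |
| 0.8 | 7/10 | 17.9% | 21.7% |
| 0.8 | 4/10 | 21.3% | 24.7% |

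At the null ORR of 15%, futile at any interim goes from 72.0% to 73-75%.

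**6. The opposite rule.** Suppose pending responses count as response and only 70% of them later confirm (assumption). In the last row's setting an immature subject then counts with probability 0.24 + 0.06/0.7 = 0.326, and P(futile at 10) falls to 12.7%. The direction of the error depends on the unstated rule.

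**The case against.** The case against is substantial, and most of it limits the size of the point.

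- **The counting rule is unstated.** A reader might infer that a Week 12 response cannot count at the look and that Table 9-3 therefore understates futility. The documents do not establish this. Section 9.5 ties confirmed ORR to the end of the cohort and speaks only of responders and response rates at the looks. Non-response is the reading that the endpoint implies, but it remains an inference. What stands is that the rule is missing.
- **Waiting is already allowed.** Two scans are a minimum, Section 8.2.3 permits extra confirmatory scans, and the wording on the 20-subject look points to a mature look. So the 20-subject look should not be presumed immature. But the text equally allows the first look to run at the minimum.
- **The 10-subject look may not happen.** The synopsis says 10 and/or 20, and Table 9-3 shows N/A for HNSCC. The NSCLC row does have a 10-subject rule, and the HNSCC rates need one.
- **Any integer cut-off flips on one response.** True, so the PPoS jump shows sensitivity and measures no harm. Frequency rests on the two assumed inputs, and at the mild end the shift is about 1 point (19.2% to 20.4%).
- **The rule is nonbinding and the cohort is exploratory.** This stands in full. A reader might infer that a promising cohort would be stopped; the plan does not provide for that.
- **The main analysis has a similar trigger.** Section 9 sets that cut-off when "all subjects who are still receiving trial treatment have at least 2 postbaseline scans performed". A reader might extend the point there, but Section 9.5 does not expressly apply the success criterion at that cut-off and the effect is immaterial. Its wording is useful mainly because it supports reading the 2 scans in Section 9.5 as postbaseline.

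**Conclusion.** The gap is real but modest. Section 9.5 permits a first look at which a Week 12 response is still pending, and it does not say how that response enters PPoS. This much follows from the text alone, as does the fact that one response moves the NSCLC call across its threshold.

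The size does not follow from the text. If pending responses count as non-response, and under the assumed timing and accrual, the NSCLC futile rate at any interim at ORR 30% is about 20-25% against the printed 19%, with the 20-subject look mature. If they count as response, the look leans the other way. In either case the effect is on a nonbinding decision statistic.

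Separately, and without any assumption about timing, the HNSCC row of Table 9-3 contradicts itself: the printed rates require a 10-subject rule that the table shows as N/A.

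**What to change.** 1. **Section 9.5, either of two rules.**
   - Count a subject at a look once that subject has had the opportunity to confirm a response: a third postbaseline scan, or a confirmatory scan at least 4 weeks after first response, or earlier PD, death, new anticancer therapy or end of trial.
   - Or keep the timing, report PPoS with pending CR/PR counted once as non-response and once as response, and defer the futility call only when the two values fall on opposite sides of the threshold.
2. **Table 9-3.** Either replace N/A with at least 1/10 for HNSCC, or keep N/A and restate that row as about 39% and 2% futile and 19% and 94% success (at ORR 10% and 25%). State that all rates assume every response is known at each look.

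No change to the Section 9 cut-off is needed.

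**Cost.** A few sentences and a rerun of one table. The first rule can delay a look by about 4-6 weeks, during which 2-6 more subjects would enter at the assumed accrual (4 weeks at one per 2 weeks; 6 weeks at one per week). The second delays only straddling calls. For NSCLC that is about 1-10% of 10-subject calls, and 1-6% of 20-subject calls if that look also runs at two scans, assuming that 70-100% of pending responses confirm. A third scan reduces the problem without removing it, since a first response at Week 18 or later would still be pending. Section 4.2.2 already requires a substantial amendment before Expansion cohort 2 opens, so the NSCLC wording can go in then.

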Statistics	For the Dose Escalation part, no formal sample size calculation was performed. The Dose Escalation part will enroll subjects from a range of cancer types. In phase 1a, a Bayesian logistic regression model (BLRM) will be used to guide the choice of GEN1053 monotherapy dose. In phase 1b, the choice of an optimal combination dose will be guided by Bayesian optimal interval method (BOIN), with a flat DL of IM, but could potentially consider different DLs of IM. For the Expansion part, no formal sample size calculation has

	been conducted, but 40 subjects would ensure at least 90% power to detect a shift to an ORR of 30% from a base rate of 10% given a 1-sided binomial test at a 5% significance level. A futility analysis will be conducted after 10 and/or 20 subjects to estimate the predictive probability of success. The probability of success estimate will be updated as data accumulates.
GCP	This trial will be conducted in compliance with the principles of the Declaration of
Compliance	Helsinki, the International Council for Harmonisation Good Clinical Practice ICH GCP
	E6(R2), and applicable regulatory requirements.

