HNSCC=head and neck squamous cell carcinoma; NSCLC=non-small cell lung cancer; ORR=objective response rate

Table 9-3Number of Responders Required at Monitoring Time to Consider Data
as a Likely "Success" (by Each Case)

Case	Data Likely Non-futile at 10 Subjects' Monitoring Time	Data Likely Non-futile at 20 Subjects' Monitoring Time	Number of Responses Required to Meet Success Criteria in 40 Subjects	True ORR	Likelihood to Consider Data Futile at any Interim	Likelihood to Meet Success Criteria at Final Analysis
A N/A	≥2/20	≥6/40	10%	48%	17%	
			25%	7%	91%	
B ≥2/10	>4/20	>9/40	15%	72%	10%	
	≥2/10	≥4/20	≥ 9/40	30%	19%	76%

ORR=objective response rate

Prior distributions: A beta (0.1, 0.9); B beta (0.15, 0.85)

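### Table 9-3 false-success rates assume every futile cohort is stopped, but Section 9.5 makes futility nonbinding; without stopping they reach 20.6% (HNSCC) and 13.5% (NSCLC), against 17% and 10% printed

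*Combined protocol and SAP*

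**What the plan says.** Section 9.5 monitors each expansion cohort, up to 40 subjects, by predictive probability of success (PPoS). At the end of a cohort, success means at least 80% posterior probability that the confirmed ORR is above p0 (10% for HNSCC monotherapy, Case A; 15% for NSCLC combination, Case B). An interim is judged futile if PPoS falls below 10% (A) or 30% (B).

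The section states the status of these thresholds twice. For A, "the threshold of 10% is not considered as a binding futility bar". For B, "However, again, the criterion is nonbinding". It also lets enrollment continue, up to 40, while the scans of the first 20 subjects are obtained and read. There is no early stopping for efficacy.

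The last column of Table 9-3, "Likelihood to Meet Success Criteria at Final Analysis", gives 17% (ORR 10%) and 91% (25%) for A, and 10% (15%) and 76% (30%) for B. The column beside it gives the chance of a futile interim: 48% and 7% for A, 72% and 19% for B. No footnote says whether a futile interim ends the cohort.

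The look schedule is described in three ways. Section 9.5 says "the PPoS will be calculated when (at minimum) 2 scans from the first 10 subjects in the Expansion cohort have been locally reviewed", followed by a look at 20, for any expansion cohort. Table 9-3 shows N/A at 10 subjects for A and at least 2/10 for B. The synopsis says "A futility analysis will be conducted after 10 and/or 20 subjects".

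**The concern.** Under a nonbinding rule, a cohort can cross the futility line, continue to 40 and still meet the success criterion. Nothing in Section 9.5 disqualifies it. A false-success rate computed as if such a cohort were always stopped leaves those paths out, so it is a lower limit and the design does not guarantee it.

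Table 9-3 gives the only operating characteristics for this rule. The 90% power statement in Section 9.2 concerns a different test: 10% against 30%, one-sided 5%. A reader weighing the risk of taking an ineffective regimen forward has only the 17% and 10%, with no sign that they depend on a stopping rule that the text disclaims.

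**Working it through.** **Inputs.** From Section 9.5 and Tables 9-2 and 9-3: priors Beta(0.1, 0.9) for A and Beta(0.15, 0.85) for B; looks at 10 and 20; final n = 40; success at posterior probability of at least 80%; futility at PPoS below 10% (A) or 30% (B).

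**Step 1: success boundaries.** After x responses in 40 the posterior is Beta(p0 + x, 1 − p0 + 40 − x).
- A: P(ORR > 0.10) is 0.648 at 5/40 and 0.807 at 6/40, so at least 6/40 is needed.
- B: P(ORR > 0.15) is 0.775 at 8/40 and 0.877 at 9/40, so at least 9/40 is needed.

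Both match Table 9-3.

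**Step 2: futility boundaries.** With x responses in n, PPoS is the beta-binomial probability that the remaining 40 − n subjects bring the total to the success boundary.
- A: 0.007 at 0/10 and 0.247 at 1/10; 0.028 at 1/20 and 0.186 at 2/20. Non-futile is at least 1/10 and at least 2/20.
- B: 0.098 at 1/10 and 0.381 at 2/10; 0.132 at 3/20 and 0.370 at 4/20. Non-futile is at least 2/10 and at least 4/20.

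**Step 3: reproduce the printed figures.** Enumerate the binomial paths through 10, 20 and 40 subjects and remove every path that falls below a futility boundary.

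| Case | True ORR | Futile: computed / printed | Success: computed / printed |
|---|---|---|---|
| A | 10% | 48.4% / 48% | 17.49% / 17% |
| A | 25% | 6.7% / 7% | 90.6% / 91% |
| B | 15% | 72.0% / 72% | 9.6% / 10% |
| B | 30% | 19.2% / 19% | 76.2% / 76% |

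All eight printed values are reproduced, so Table 9-3 treats futility as always followed.

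**Step 4: no stopping.** If futility is never acted on, success depends only on the final count X, with X ~ Binomial(40, ORR).

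| Case | True ORR | P(success), no stopping | Printed | Gap from computed value in Step 3 |
|---|---|---|---|---|
| A | 10% | P(X ≥ 6) = 20.6% | 17% | 20.6 − 17.5 = 3.1 points |
| A | 25% | P(X ≥ 6) = 95.7% | 91% | 95.7 − 90.6 = 5.1 points |
| B | 15% | P(X ≥ 9) = 13.5% | 10% | 13.5 − 9.6 = 3.9 points |
| B | 30% | P(X ≥ 9) = 88.9% | 76% | 88.9 − 76.2 = 12.7 points |

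The gap is the probability of crossing a futility boundary and still reaching the success count.

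**Step 5: the Case A look at 10.** Step 3 used at least 1/10 for A, where Table 9-3 prints N/A. With only the 20-subject look, always followed, A gives futile 39.2% and success 19.3% at ORR 10%, and futile 2.4% and success 94.3% at 25%. None of these matches the table. The printed A row therefore contains a 10-subject boundary that the table does not show. Section 9.5 also implies one, since PPoS at 0/10 is 0.7%, well below its 10% threshold.

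**The case against.** The strongest defense is that nothing was miscalculated. Success with the futility rule followed is a legitimate operating characteristic, and it sits beside the column giving the chance of a futile interim, so both can be read as describing the same monitored design. That stands: the fault is an unstated assumption that conflicts with the text.

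A reader might go further and infer that the printed power is wrong and should be replaced by 96% and 89%. The documents do not support this. Nonbinding does not mean always ignored. The no-stopping figures assume that the sponsor never acts on its own rule, which makes them the most optimistic power. A nonbinding rule is normally reported with false success computed ignoring futility and power computed with it applied, and on that convention 91% and 76% are the right power figures.

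The rule is also exploratory. Section 9.1 disclaims confirmatory testing, Section 9.2 describes a preliminary assessment of efficacy, ORR is a secondary endpoint, and Section 4.1 has the safety committee decide progression on benefit-risk. No formal alpha is breached and no automatic go follows from 6/40 or 9/40. This limits the severity but does not remove the mismatch.

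The synopsis wording can be defended as covering two cohorts with different look schedules, which would fit the N/A in Table 9-3. But the printed Case A figures cannot come from a cohort without a 10-subject look, so the discrepancy remains.

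**Conclusion.** The false-success rates in Table 9-3 are understated for the nonbinding rule that Section 9.5 describes. Depending on how often futility is acted on, they run from 17.5% to 20.6% for HNSCC at ORR 10% and from 9.6% to 13.5% for NSCLC at ORR 15%. Against the printed 10%, the NSCLC upper limit is 35% higher in relative terms (13.5/10). A figure of about 40% comes only from dividing by the unrounded 9.6% and should not be quoted as the excess over the printed value.

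Power runs from 90.6% to 95.7% (HNSCC, ORR 25%) and from 76.2% to 88.9% (NSCLC, ORR 30%). The printed values are the conservative ends and can stay.

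Separately, the N/A for HNSCC at 10 subjects is inconsistent with the figures in its own row.

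These results assume independent responses with a common true ORR, all 40 subjects counted, and looks at exactly 10 and 20. Severity is minor to moderate: no boundary, sample size or estimate changes.

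**What to change.** 1. Label the existing success column of Table 9-3 *if the futility rule is always followed*.
2. Add the false-success rates without futility stopping, 21% (A, ORR 10%) and 14% (B, ORR 15%), and name them as the governing figures for a nonbinding rule.
3. Keep 91% and 76% as the power figures. Optionally show 96% and 89% as the no-stopping upper bound.
4. Settle the Case A look at 10. If it takes place, replace N/A with at least 1/10, and the printed 48/17 and 7/91 stand. If it does not, the futility-followed row becomes 39/19 and 2/94, with the power in item 3 changed to match, and Section 9.5 should say that A has only the 20-subject look. The no-stopping figures are the same either way.
5. Align the synopsis wording on the looks with the resolved schedule, and carry the same labels into the SAP, which Section 9 leaves to be finalized before database lock.

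The cost is a column label, two to four added numbers and a few words. The stated false-success rates become slightly less favorable. Thresholds, success boundaries and the 40 subjects per cohort are unchanged, and futility can remain nonbinding.

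### Table 9-3 prints no 10-subject futility boundary for the HNSCC cohort, but the operating characteristics in that row hold only with a boundary of ≥1/10

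*Combined protocol and SAP*

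**What the plan says.** Section 9.5 applies interim monitoring to every Expansion cohort: "The efficacy in each Expansion cohort will be monitored utilizing the Bayesian efficacy monitoring via predictive probabilities". On the first look it says that "the PPoS will be calculated when (at minimum) 2 scans from the first 10 subjects in the Expansion cohort have been locally reviewed"; a second look follows at 20 subjects, and the maximum is 40. For HNSCC the criterion is "If the predicted probability of success is less than 10% the monotherapy Expansion cohort is judged as likely being" futile. For NSCLC, "For the combination therapy Expansion cohort, a 30% threshold determines whether further investigation is judged" futile or not. Both thresholds are nonbinding; for monotherapy, "the threshold of 10% is not considered as a binding futility bar". The final criterion is set on the posterior scale: "the success criteria are defined as the posterior probability that the confirmed ORR exceeds the ineffective ORR threshold" p0, with at least 80% probability.

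Table 9-3 turns these rules into responder counts and operating characteristics, with the futility column headed "Likelihood to Consider Data Futile at any Interim":

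| Case | At 10 | At 20 | Final | True ORR | Futile at any interim | Success |
|---|---|---|---|---|---|---|
| A (HNSCC, p0 = 10%) | N/A | ≥2/20 | ≥6/40 | 10% | 48% | 17% |
| | | | | 25% | 7% | 91% |
| B (NSCLC, p0 = 15%) | ≥2/10 | ≥4/20 | ≥9/40 | 15% | 72% | 10% |
| | | | | 30% | 19% | 76% |

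The footnote gives the priors as Beta(0.1, 0.9) for A and Beta(0.15, 0.85) for B. The synopsis (Section 1.1, Statistics) is looser and places the futility analysis after 10 and/or 20 subjects.

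**The concern.** The text gives the HNSCC cohort a look at 10 subjects with a 10% PPoS threshold, while the table gives it no responder count at that look. Section 9.5 sends the reader to Table 9-3 for those counts, so the table is what a team would have in hand when the first 10 HNSCC subjects have been scanned. If N/A is taken at face value, 0/10 raises no flag. If the printed probabilities are taken at face value, 0/10 does raise one. Either the decision threshold or the stated operating characteristics are wrong.

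There is a smaller second issue. The success column assumes that a futile reading ends the cohort, whereas the text makes both thresholds advisory and allows enrollment to continue.

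**Working it through.** **Inputs** (all from Section 9.5 and Tables 9-2 and 9-3): looks at 10 and 20 subjects, final analysis at 40; Case A prior Beta(0.1, 0.9), p0 = 10%, p1 = 25%; success if the posterior probability of ORR > p0 is at least 80%; futile if PPoS < 10% (A) or < 30% (B); no early stopping for efficacy.

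**1. Final rule, Case A.** The posterior after r/40 is Beta(0.1 + r, 0.9 + 40 − r). P(ORR > 10%) is 0.648 at r = 5 and 0.807 at r = 6, so success needs ≥6/40, as printed.

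**2. Interim boundaries, Case A.** With x responders among n subjects, PPoS = P(Y ≥ 6 − x), where Y ~ Beta-binomial(40 − n, 0.1 + x, 0.9 + n − x).

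| Data | PPoS | Against 10% |
|---|---|---|
| 0/10 | 0.7% | futile |
| 1/10 | 24.7% | not futile |
| 1/20 | 2.8% | futile |
| 2/20 | 18.5% | not futile |

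The stated rule therefore gives ≥1/10 and ≥2/20. The 20-subject count agrees with the table; the 10-subject count is the one printed as N/A.

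**3. Futility probability, Case A.** This can be done by hand.

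*As printed (look at 20 only):* P(X₂₀ ≤ 1) = (1 − p)²⁰ + 20p(1 − p)¹⁹.
- p = 0.10: 0.1216 + 0.2702 = 0.392
- p = 0.25: 0.0032 + 0.0211 = 0.024

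*With ≥1/10 as well:* P(X₁₀ = 0) + P(X₁₀ = 1) × P(no responder in the next 10).
- p = 0.10: 0.3487 + 0.3874 × 0.3487 = 0.484
- p = 0.25: 0.0563 + 0.1877 × 0.0563 = 0.067

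The table prints 48% and 7%.

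**4. All four Case A figures**, by exact enumeration over 10 + 10 + 20 subjects, with a futile reading ending the cohort:

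| Boundaries | Futile, 10% | Futile, 25% | Success, 10% | Success, 25% |
|---|---|---|---|---|
| Table 9-3, stated | 48% | 7% | 17% | 91% |
| N/A, ≥2/20, ≥6/40 | 39.2% | 2.4% | 19.3% | 94.3% |
| ≥1/10, ≥2/20, ≥6/40 | 48.4% | 6.7% | 17.5% (0.1749) | 90.6% |

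Every printed figure misses under the printed boundaries and matches under ≥1/10. A grid of alternatives (none, ≥1 or ≥2 at 10; ≥1, ≥2 or ≥3 at 20; ≥5, ≥6 or ≥7 at 40) gives no other combination matching all four. With no look at 10, the futility probability at ORR 10% is 12.2%, 39.2% or 67.7% for 20-subject boundaries of ≥1, ≥2 or ≥3, never 48%.

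**5. Check of the method on Case B.** PPoS is 9.8% at 1/10, 38.1% at 2/10, 13.2% at 3/20 and 37.0% at 4/20, which gives ≥2/10 and ≥4/20 against the 30% threshold. The posterior is 0.775 at 8/40 and 0.877 at 9/40, which gives ≥9/40. Enumeration gives futility 72.0% and 19.2%, success 9.6% and 76.3%, against the printed 72%, 19%, 10% and 76%. The method is therefore the table's own, and the mismatch is confined to Case A.

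**6. Success if the nonbinding rule is not followed** (plain binomial tail at 40): A, 20.6% at ORR 10% and 95.7% at 25%; B, 13.5% at 15% and 88.9% at 30%.

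**The case against.** The strongest reply is that little depends on this cell. The thresholds are nonbinding, the plan disclaims confirmatory testing (Section 9.1), ORR is a secondary endpoint, and the final rule, the 20-subject boundary, the prior and the PPoS threshold are all sound. A team that follows the text and computes PPoS at 10 subjects would find 0.7% after 0/10 and flag futility whatever the table says. Even if it did not, a cohort with 0/10 is flagged at 20 unless at least two of the next ten respond. All of that stands, and it limits the consequence. It does not remove the contradiction: how often data are judged futile does not depend on whether the cohort then stops, so nonbinding status cannot turn 39% into 48%.

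A second reply is that the synopsis wording may allow a 20-subject look only for HNSCC. That is possible, but Section 9.5 exempts no cohort, and all four probabilities would then be wrong. The sponsor has to say which was meant.

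A third is that success probabilities computed with futility stopping are a legitimate presentation. That is right: leaving out the no-stopping values is a gap in the information given and not an arithmetic error.

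**Conclusion.** The Case A row of Table 9-3 is wrong as written. The evidence points to the N/A cell: the plan's own 10% rule yields ≥1/10, and the four printed probabilities already include that boundary. As printed, the row understates the monitoring. At a true ORR of 10%, 0/10 arises with probability 0.9¹⁰ = 34.9%, and the table shows no flag although PPoS is 0.7%. If N/A is what the sponsor intended, the futility probability at ORR 10% is overstated by about 9 points (48% against 39.2%), and false success is understated by about 2 (17% against 19.3%).

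The result rests on the stated prior, thresholds and look sizes, on independent binomial responses, and on a futile reading ending the cohort, as the table itself assumes. It also takes N/A as the printed 10-subject entry for Case A; the table's layout is damaged in the text available, but the entry sits in parallel with Case B's ≥2/10. The consequence is moderate because the rule is advisory, but the correction should be made before the HNSCC cohort opens.

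**What to change.** Replace N/A with ≥1/10 in the Case A row; the four probabilities then stand unchanged. If the sponsor intends no 10-subject look for HNSCC, keep N/A, restate the row as futility 39% and 2%, success 19% and 94%, and exempt that cohort from the first look in the text of Section 9.5. In either case, bring the and/or wording in the synopsis into line.

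As a supplement, add a column or footnote with the success probabilities when futility is not acted on: A, 21% and 96%; B, 14% and 89%.

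The cost is one table cell, or one row and a sentence, plus a footnote. Nothing changes in sample size, assessments or conduct.
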